Additionally, advances in measurement techniques and an understanding of ocular physiology suggest the need for updated normative data that reflect current population characteristics and incorporate modern assessment methodologies.

Given these limitations, there is a pressing need to establish population-specific normative data for the field of binocular single vision in Singapore's adult population. This would not only provide more relevant reference values for clinical assessment but also potentially improve the accuracy of diagnosis and monitoring of various ocular conditions in our local context.

Study Objectives

The primary purpose of this pilot study is to address these gaps in current clinical practice through two main objectives. First, we aim to establish the normative range of the field of binocular single vision specifically for adults in Singapore, creating a locally relevant reference

standard. This will provide clinicians with more appropriate benchmarks for assessing their patients.

Secondly, we seek to determine whether a significant difference exists between these local normative values and the currently used standards established by Feibel & Roper-Hall in 1974. We hypothesise that there will be a significant difference in the normative range of the field of binocular single vision in our current adult population in Singapore compared to the historical standards. This hypothesis is based on the understanding that genetic, environmental, and temporal factors may influence ocular characteristics.

The findings from this study could have substantial clinical implications. If significant differences are identified, it would justify the adoption of new, population-specific normative values for clinical practice in Singapore. This could lead to more accurate assessment and monitoring of subjects, potentially improving the quality of eye care delivered to our population. Furthermore, this study could serve as a model for other Asian countries to establish their population-specific normative values, contributing to the broader field of ophthalmology in the region.

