2. STUDY DESIGN

This research will be conducted as a single-centre, pilot study at Tan Tock Seng Hospital, designed as an observational investigation regulated under the Human Biomedical Research Act (HBRA) of Singapore. This study will employ a cross-sectional design, with each participant completing all assessments in a single visit lasting approximately 60 minutes. This approach has been chosen to minimise participant burden while ensuring comprehensive data collection.

The study will span a total duration of one year, with active data collection scheduled from 1 November 2025 to 31 October 2026. This timeline allows for adequate recruitment, data collection, and subsequent analysis while accounting for potential scheduling challenges and the need for careful quality control of the collected data. The single-visit design also helps minimise dropout rates and ensures consistency in data collection procedures.

Study Design:

Study population: This study aims to recruit a balanced sample of adult participants from Singapore's population, with a target enrolment of 32 participants, equally distributed between males and females (16 of each gender) and of Asian descent. This sample size has been

carefully determined to provide sufficient statistical power while remaining feasible within the study's resources and timeline.

Participants will be recruited primarily by word of mouth at the TTSH Ophthalmology Specialist Outpatient Clinic's, focusing on accompanying next-of-kin of existing patients, TTSH staff members, or any other available healthy volunteers after meeting the inclusion and exclusion criteria. The recruitment process will be conducted with careful attention to avoiding any coercion or undue influence, particularly in cases involving dependent relationships. All potential participants will be given adequate time to consider their participation and will be required to provide informed consent in the presence of a witness in compliance to the Declaration of Helsinki, as well as other prevailing laws and guidelines regulating clinical research.

Inclusion Criteria:

1. Age: 21 to 59 years old
2. Gender: Males or females
3. Ethnicity: Asian descent.
4. Language comprehension: Able to understand verbal spoken instructions in:
 - British/American English
 - Mandarin Chinese
 - Bahasa Melayu
5. Protocol compliance: Ability to comply with the study protocol, as determined by the investigator's judgment

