6. Consent capacity: Must be able to understand and provide informed consent, with signed informed consent form required before any study assessments

Exclusion Criteria:

1. Communication barrier: Unable to understand verbal spoken instructions
2. Medical history:
 - Any facial trauma
 - Any ocular trauma
 - Any head trauma
 - Any history of ocular disease
 - Any history of ocular surgery
 - Systemic condition(s)

3. Near visual acuity:

- Right eye & Left eye monocularly, binocularly unaided near vision: worse than N6 at 40cm from participant's nose

4. Ocular alignment:

- Prism cover test at near (30cm) of equal or greater than 10 prism diopters at these positions of gaze:

- Primary gaze
- Right gaze
- Left gaze
- Up gaze
- Down gaze

5. Extraocular movement:

- Extraocular movement of over-action or under-action of equal or greater than 0.5 in any of the nine cardinal positions of gaze

6. Confrontational Visual field:

- Abnormal monocular visual field on confrontational visual field test

7. Hess chart test

- Abnormal or asymmetry in pattern of extraocular muscle action in Hess chart test

8. Pregnant woman will be excluded from this study.

Study Procedure:

This cross-sectional study will involve 1 study visit.

Pre-specified clinical outcome: The primary outcome is the establishment of a normative range of field of binocular single vision measurements in Singapore adults. These measurements will be taken using the Takagi MT-325UD Projection Perimeter. The secondary outcome is the comparison with the normal boundary of the established field of binocular single vision by Feibel & Roper-Hall (1974) and the analysis of any significant differences between the two sets of measurements.

Clinical Validation will be a cross-sectional study design to determine the normative range of the field of binocular single vision measurements in participants who are Singapore adults focusing on accompanying next-of-kin of existing participants and TTSH staff members after meeting the inclusion and exclusion criteria.

Research Procedures:

1) *Medical history assessment*

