All examinations will be performed by trained orthoptists, with results recorded immediately in standardised documentation forms. The testing sequence will remain consistent across all participants, and any exclusion criteria met will be documented with specific measurements and observations.

As part of the clinical evaluation of participants during the analysis phase, access and extraction of data will be limited to TTS's NGEMR and Zeiss Forum Viewer. Clinical information collected for this study would include medical & ocular histories along with prior visual assessments documented by orthoptists.

Additionally, NEHR cannot and will not be used for research. Access of medical records for the purpose of data collection will also be limited to the period dated from 1 November 2025 to 31 October 2026. Clinical information/data collected will be done once off during, or retrospectively after the study visit.

Sample size calculation

This is a pilot study. Due to resource constraints, a total of 32 healthy participants will be recruited for this study.

Based on the literature, the standard deviation (SD) of normal values for the selected binocular single vision measure ranges from 5.3 to 6.9. Assuming an SD of 6 in our study, a sample size of 29 will allow us to estimate the mean of normal values with a precision of 2.2 at the 95% confidence level. We expect drop out rate to be no more than 10%, 32 participants will be sufficient.

References:

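### The sample size is called sufficient for a study of a normative range, but the only supporting figure is the precision of the mean, and no power is calculated

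*Protocol*

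**What the plan says.** Under Study Objectives the protocol states that "we aim to establish the normative range of the field of binocular single vision specifically for adults in Singapore", and adds: "This will provide clinicians with more appropriate benchmarks for assessing their patients". The pre-specified clinical outcome under Study Procedure agrees: "The primary outcome is the establishment of a normative range of field of binocular single vision measurements in Singapore adults". The secondary outcome is a comparison with the 1974 boundary, and Study Objectives hypothesises a significant difference.

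The size is justified in two places.

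- **Study Design, Study population:** the target of 32 was "carefully determined to provide sufficient statistical power while remaining feasible within the study's resources and timeline".
- **Sample size calculation:** "Due to resource constraints, a total of 32 healthy participants will be recruited for this study". The literature SD "ranges from 5.3 to 6.9" (no unit given) and an SD of 6 is assumed. With that SD, "a sample size of 29 will allow us to estimate the mean of normal values with a precision of 2.2" at 95% confidence. The section ends: "We expect drop out rate to be no more than 10%, 32 participants will be sufficient".

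The protocol gives no other figure in support of the sample size.

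**The concern.** The quantity that was sized is not the quantity the study sets out to deliver. A mean and a range are different targets. The limits of an SD-based range depend on both the sample mean and the sample SD, so they are less certain than the mean alone. A reader who sees 2.2 followed by a statement that 32 is enough will take 2.2 as the precision of the study's main product.

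The power claim is a separate gap. Power belongs to a test, and the only candidate is the comparison with the historical boundary. For that comparison the protocol gives no difference to detect, no significance level and no power.

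This matters because of the intended use. Study Objectives says the range will serve clinicians as a benchmark and that, if it differs from the 1974 standard, new local values would be justified. The Background criticises that standard for its small sample and doubtful reliability. The protocol should therefore be open about how reliable its own limits will be.

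**Working it through.** **Inputs from the protocol (Sample size calculation):** SD 6, literature range 5.3 to 6.9; 29 evaluable; 95% confidence; drop-out up to 10%; 32 recruited.

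**Assumptions not in the protocol:** one summary measure per participant, normally distributed values, and a range of the form mean ± k × SD.

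**1. The protocol's own figure.** The half-width for the mean is 1.96 × SD / √n.
- SD 6, n = 29: 1.96 × 6 / √29 = 2.18, which rounds to 2.2.
- In reverse: (1.96 × 6 / 2.2)² = 28.6, so 29.
- SD 5.3 gives 1.93 and SD 6.9 gives 2.51.

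The stated figure reproduces.

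**2. Drop-out.** 32 × 0.9 = 28.8, and 32 − 3 = 29. Strict inflation gives 29 / 0.9 = 32.2, hence 33. The difference of one is immaterial.

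**3. Precision of a range limit.** The approximate half-width is 1.96 × SD × √(1/n + k² / (2(n − 1))).

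For k = 1.96 and n = 29, the bracket is 1/29 + 3.8416/56 = 0.0345 + 0.0686 = 0.1031, with square root 0.3211. At SD 6 this gives 1.96 × 6 × 0.3211 = 3.78.

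| Quantity (n = 29) | SD 5.3 | SD 6 | SD 6.9 | Ratio to mean |
|---|---|---|---|---|
| Mean | 1.93 | 2.18 | 2.51 | 1 |
| Limit, mean ± 1.96 SD | 3.34 | 3.78 | 4.34 | 1.73 |
| Limit, mean ± 1.645 SD | 2.99 | 3.38 | 3.89 | 1.55 |

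The share of the variance of a mean ± 1.96 SD limit that comes from estimating the SD is 0.0686 / 0.1031 = 67%. The 2.2 omits this part.

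With no drop-out (n = 32, SD 6), the half-width is 2.08 for the mean and 3.59 for each mean ± 1.96 SD limit.

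**4. Check on the approximation.** At n = 29 and a sample SD of 6, the exact noncentral-t 95% interval for the upper limit runs from mean + 8.66 to mean + 16.65, around a point estimate of mean + 11.76. Its average half-width is (16.65 − 8.66) / 2 = 4.0, so 3.8 does not overstate the uncertainty.

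**5. Power, for illustration only.** Take a one-sample, two-sided 5% t test of the mean against a fixed historical value, with n = 29 and SD 6. A difference of about 3.2 is detectable with 80% power. For a difference of 2.2, power is about 48%. The protocol says nothing about which difference matters, so its power claim cannot be assessed.

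**The case against.** The best defence is that the sample size section is accurate and limited in scope. It labels 2.2 as the precision of the mean, and its closing sentence can be read as saying only that 32 leaves about 29 after drop-out. The study is called a pilot, and both places that justify the size mention resources, so the apparent conflict between a size determined for power and one set by resources is partly one of tone. That much is fair, and it supports keeping 32 on feasibility grounds. It does not supply a power calculation, and it does not make the precision of a mean describe a range.

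A second objection is that the range is undefined, so 3.8 belongs to one reading among several. The protocol also speaks of a normal boundary. If the range meant only an average boundary, 2.2 would be the right figure. For percentile or minimum-to-maximum limits, none of the limit figures above apply. This stands as a condition on the size of the effect. It does not remove the mismatch, because both the objective and the primary outcome say range. A separate analysis plan may define the range, but it cannot support claims of sufficiency and power that the protocol makes on other grounds.

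Third, a symmetric 3.8 hides some asymmetry: the exact interval is about −3.1 and +4.9 around the upper limit. That is true. An approximate figure is adequate for planning, and the reported intervals can be exact.

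**Conclusion.** The concern holds. The protocol asserts sufficient power without any power calculation, and it calls 32 participants sufficient on the strength of a figure for the mean when the primary outcome is a range. The arithmetic behind 2.2 is correct, but it answers a different question.

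If the range is mean ± 1.96 SD of normal values with 29 evaluable participants, each limit is known to about ± 3.8 at SD 6 (3.3 to 4.3 over SD 5.3 to 6.9), or 1.73 times the stated 2.2. For a central 90% range the figure is 3.4 (3.0 to 3.9), a ratio of 1.55. The numbers depend on the range definition and on normality. The missing power calculation and the mismatch between mean and range do not.

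This should be fixed. It bears on how much weight the limits can carry in practice, not on whether the study can proceed.

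**What to change.** Keep 32 participants and the feasibility basis.

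**Sample size calculation.** Replace the precision and sufficiency sentences with wording such as:

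> With 29 evaluable participants and SD 6, the 95% CI half-width for the mean is 2.2. Taking the normative range as mean ± 1.96 SD and values as normal, the approximate 95% CI half-width of each limit is 3.8 (3.3 to 4.3 for SD 5.3 to 6.9). The limits are provisional and each will be reported with its 95% CI. Recruiting 32 allows for up to 3 drop-outs.

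If the sponsor chooses another definition of the range, its own figure should replace 3.8.

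**Study Design, Study population.** Replace the power claim with:

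> The sample size is set by feasibility; the expected precision is given in the sample size section.

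**Cost.** Two wording changes and a confidence interval for each reported limit. No extra participants and no change in conduct are needed. The sponsor must commit to the range definition that the figure assumes, and the stated precision will look less favourable.

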A comprehensive medical history will be obtained from each participant through a structured interview. The investigator will specifically inquire about any history of facial trauma, ocular trauma, head trauma, ocular disease, ocular surgery or any systemic condition(s), documenting the nature, timing, and severity of any reported incidents. Particular attention will be paid to any previous ocular diseases and surgical interventions. All responses will be recorded in standardized case report forms, with detailed documentation of the type, date, and outcome of any reported conditions or procedures. Participants should not have any history of facial trauma, ocular trauma, head trauma, ocular disease, ocular surgery or any systemic condition(s). This thorough screening is essential to ensure participants meet the study criteria for establishing normative values.

2) *Near Visual Acuity Testing*

Near visual acuity will be assessed right eye and left eye monocularly & binocularly using a standard near vision chart held at 40cm from the participant's nose. Testing will be conducted under standardized lighting conditions with monocularly and binocularly and unaided. A measuring stick will be used to maintain the precise testing distance. The examiner will record the smallest line that can be read accurately, with participants required to achieve N6 or better to be included in the study. Any participant with near vision worse than N6 will be excluded from the study.

3) *Ocular Alignment Assessment*

A prism cover test will be performed at near of approximately 30cm from participant's nose to evaluate ocular alignment. The examiner will systematically assess alignment in five positions of gaze: primary gaze (straight ahead), right gaze, left gaze, up gaze, and down gaze. Measurements will be taken using loose prisms or a prism bar, with deviations recorded in prism diopters. Any deviation equal to or greater than 10 prism diopters in any of the five positions of gaze will result in exclusion from the study. The examiner will ensure consistent testing distance using a measuring stick and maintain standardized testing conditions throughout the assessment.

4) Extraocular Movement Testing

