Extraocular muscle function will be examined by having the participant follow a fixation target through the nine cardinal positions of gaze. The examiner will assess and grade any overaction or underaction of the extraocular muscles using a standardized scale, where 0 represents normal movement. Participants demonstrating overaction or underaction equal to or greater than 0.5 units in any direction will be excluded from the study. The examination will be conducted methodically, ensuring smooth pursuit movements are carefully observed and documented.

5) Confrontational Visual Field Testing

Monocular confrontational visual field testing will be performed separately for each eye. The examiner will sit at one meter distance, directly facing the participant at eye level. Each quadrant of the visual field will be tested systematically using standardized targets, while the participant maintains fixation on the examiner's nose. Any abnormality in the visual field will be documented and will result in exclusion from the study. The testing sequence will remain consistent for all participants to ensure standardization of the assessment.

6) Hess Chart Testing

The Hess chart test will be conducted using a standard Hess screen at the recommended testing distance. This test will evaluate the action of each extraocular muscle, with results plotted on the Hess chart. The examiner will assess for any asymmetry or abnormality in the pattern of extraocular muscle action. Any abnormal findings on the Hess chart will be documented in detail and will result in exclusion from the study. The test will be performed following standardized protocols to ensure consistency and accuracy of results.

7) Field of binocular single vision

Participants perform the field of binocular single vision test binocularly and pursue a single round light stimulus presented in the bowl of the Takagi MT-325UD Projection Perimeter, and participants will need to look and follow through the single light stimulus as it moves throughout the bowl, and participants will press the buzzer if two distinct light stimuli are seen. Scores will be recorded and plotted on the recording sheet based on participants' responses during the test. Eye dilation will not be required for this research study.

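### Do failures at the post-consent eligibility tests use up the 32 places and leave fewer than the 29 needed?

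*Protocol*

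**What the plan says.** The Sample size calculation in the Protocol states: "Assuming an SD of 6 in our study, a sample size of 29 will allow us to estimate the mean of normal values". The 95% half-width it reports for this is 2.2. It takes SD 6 from a literature range of 5.3 to 6.9, describes the study as a pilot limited by resources, and recruits 32 healthy people. The margin is justified thus: "We expect drop out rate to be no more than 10%, 32 participants will be sufficient".

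Section 2 (Study Design) puts every assessment into one visit of about an hour, says this keeps dropout low, and sets the enrolment target at 32, half of each sex. Inclusion criterion 6 requires consent first: "with signed informed consent form required before any study assessments".

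Research Procedures 1 to 6 then cover history, near acuity, prism cover test, eye movements, confrontation field and Hess chart. The field of binocular single vision comes last, as procedure 7. Failing a test ends participation. For near acuity: "Any participant with near vision worse than N6 will be excluded from the study". For the Hess chart: "Any abnormal findings on the Hess chart will be documented in detail and will result in exclusion from the study".

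The protocol gives no expected screen-failure rate and no rule on replacement.

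**The concern.** A dropout allowance normally covers people lost between enrolment and the outcome. Here that interval is part of one visit, so ordinary dropout should be rare. What can remove a consented person is failure at any of six screens, some of them strict on their face: unaided N6 in each eye for people up to 59, any motility deviation of 0.5 or more, any Hess asymmetry, and an unqualified exclusion for systemic conditions. The procedures call such people participants who are then excluded, which makes it sound as though they had already taken a place.

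If they had, the 10% would be aimed at the wrong source of loss. More than 3 failures among 32 would take the evaluable number below 29, and the normative mean would be estimated less precisely than stated. The 16-per-sex balance would be exposed in the same way.

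**Working it through.** **Inputs.** From the Sample size calculation: SD 6 (range 5.3 to 6.9), half-width 2.2, 95% confidence, 29 evaluable, 32 recruited, loss of at most 10%. The documents give no screen-failure rate, so every loss rate below other than that 10% is an assumption.

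**1. The plan's own figure.** n = (1.96 × SD / d)² = (1.96 × 6 / 2.2)² = 28.57, rounded up to 29. The half-width at 29 is 1.96 × 6 / √29 = 2.18. For the allowance, 29 × 1.10 = 31.9, so 32; dividing instead gives 29 / 0.90 = 32.2, so 33. One person's difference is immaterial. The stated numbers reproduce with the normal quantile. With the t quantile the half-width at 29 is 2.28, and 32 are needed for 2.2.

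**2. The margin.** 32 − 29 = 3 losses, or 3/32 = 9.4%. A fourth loss leaves 28, and 1.96 × 6 / √28 = 2.22, which still rounds to the stated 2.2.

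**3. The adverse reading: all losses, screen failures included, come out of the 32.** The chance of keeping at least 29 is P(X ≤ 3) with X ~ Binomial(32, p). The half-width uses SD 6 and the expected evaluable number rounded down.

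| Assumed total loss | Expected evaluable | P(at least 29) | Half-width |
|---|---|---|---|
| 5% | 30.4 | 0.93 | 2.15 (n = 30) |
| 10% | 28.8 | 0.60 | 2.22 (n = 28) |
| 15% | 27.2 | 0.27 | 2.26 (n = 27) |
| 20% | 25.6 | 0.09 | 2.35 (n = 25) |
| 30% | 22.4 | 0.005 | 2.51 (n = 22) |

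The probabilities fall fast because 29 is treated as a cliff. The precision changes slowly because it depends on √n.

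**4. Comparison with the uncertainty the plan already accepts.** At n = 29 the half-width is 1.96 × 5.3 / √29 = 1.93 at the low end of the quoted SD range and 1.96 × 6.9 / √29 = 2.51 at the high end. Losing 30% of the sample at SD 6 gives 2.51, no worse than the upper SD with no shortfall below 29.

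**5. Which reading the text supports.** Four places favour counting eligible people only:
- the recruitment paragraph in Section 2, where volunteers are taken once they meet the criteria;
- the clinical validation paragraph under Study Procedure, which repeats this;
- Research Procedure 2, where reaching N6 is a condition of being included;
- the Sample size calculation, where the 32 are described as healthy.

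On the other side stand inclusion criterion 6, with consent before assessments, and the word participant for people later excluded. These fit together without contradiction if a person consents, is screened, and is counted on passing. Consent before testing is not the same as occupying one of the 32 places.

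**The case for a change.** The strongest case for a change is that the enrolment target and its justification are fixed in the protocol, so a later analysis plan cannot settle who counts. The people excluded in Research Procedures 2 to 6 are called participants and have signed consent, and no replacement rule is written. Two members of staff could therefore stop enrolment at different points. Even at the protocol's own 10% ceiling, the expected evaluable number is 28.8 and the chance of missing 29 is 40%.

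Part of this stands. The count is undefined, and a sentence defining it would be harmless. The rest is weaker. The 40% treats a ceiling as the expected rate and treats 28 as a failure, although 28 still gives 2.22. Any allowance set close to the expected loss will often be exceeded by one or two. Loss rates of 20% or 30% have no source in the documents, and the people approached are healthy volunteers, staff and relatives. Screen failures will in any case be visible, because the paragraph after the Research Procedures requires each exclusion criterion met to be recorded with its measurements.

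**Conclusion.** The concern does not call for a change. Read in the way its own text favours, the plan counts eligible people. The 10% then covers field tests that are incomplete or unusable, and 29 evaluable with a half-width of 2.2 (normal quantile, SD 6) is what the plan delivers. What remains is a detail that a study team would fill by screening until 32 people, 16 per sex, have passed.

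If the team instead stopped at 32 consents, the cost would be a wider interval: 2.22 with 28 evaluable, or 2.35 with 25. The latter is about 8% wider than at 29, since √(29/25) = 1.08. In a pilot whose size is set by resources, no decision in the protocol turns on 2.2 versus 2.35. Restating the precision in advance would require a screen-failure rate that the documents do not supply.

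This conclusion assumes that screen failures are replaced. It would need another look only if the sponsor confirmed that 32 is a cap on consents and expected a high failure rate.
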